Principal Investigator: [name]

Study Number: 17-00051

NCT Number: NCT03183778

1) **Protocol Title**

Use of patiomer to transition chronic kidney disease patients with hyperkalemia to a plant-rich diet

2) **Objectives**

The purpose of this proof-of-concept controlled-feeding study is to determine whether patiomer (Veltassa®, Relypsa, Inc., Redwood City, CA) can be used to maintain normal serum potassium concentrations in chronic kidney disease (CKD) patients who are transitioned to a plant-rich diet. We hypothesize that patiomer can be titrated to maintain serum potassium concentrations in the normal range, allowing CKD patients to consume a plant-rich diet without developing hyperkalemia. If successful, we plan to conduct a randomized clinical trial to determine the quality of life and health outcomes of CKD patients with hyperkalemia undergoing an intensive behavioral intervention to promote a low-potassium diet, or a plant-rich diet plus patiomer.

3) **Background**

An estimated 22.5% of adults 60 years and older in the U.S. have stages 3-5 CKD¹. Individuals with stages 3-5 CKD are at increased risk of high blood potassium concentrations (hyperkalemia), which in severe cases can disrupt the normal contractility of the heart². Several factors are thought to contribute to hyperkalemia in CKD patients, in particular diabetes, dietary potassium intake, and medications that inhibit the renin-angiotensin-aldosterone system (RAAS inhibitors, which include angiotensin converting enzyme inhibitors and angiotensin 2 receptor blockers; ACEi and ARBs)^{3,4}. Given the potential health consequences of hyperkalemia, stages 3-5 CKD patients, even those without hyperkalemia, are often directed to follow a low-potassium diet⁴.

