a) Change in medications that alter potassium homeostasis (e.g., RAAS inhibitors, diuretics, β -blockers) in the last month

b) Diagnosed with bowel diseases or syndromes (e.g., bowel obstruction, major GI surgery, short-bowel syndrome, irritable bowel syndrome, inflammatory bowel disease, chronic diarrhea)

c) Dietary restrictions (e.g., allergies) or otherwise unable/unwilling to adhere to study diets (excludes dietary restrictions on high-potassium foods)

d) Pregnant (females) or planning to become pregnant (males and females) during the study

If at any point during the study (including baseline) a participant has moderate-severe hyperkalemia (potassium \geq 6.5mEq/L), or if a participant becomes pregnant during the study, they will be withdrawn from the study.

Inclusion of women and minorities

Given the pilot nature of the intervention and small sample size (n=10), the study population will not be representative of the CKD population, and will have insufficient power to detect differences in intervention effects by sex and race/ethnicity. To our knowledge, plant-rich diets, such as those being investigated in this study, have similar health effects by sex and race/ethnicity. No individual will be excluded from the study on the basis of sex or race/ethnicity alone, and we will attempt to obtain a sample that reflects the demographics of our source population.

5) Study-Wide Number of Subjects

We will recruit a total of 10 individuals to the study. We have secured the support of the New York Harbor VA Healthcare System, which served approximately 250 non-dialysis CKD patients in the New York City area, as well as the Division of Nephrology at NYU Langone Health. It is estimated that approximately 10% of these patients have hyperkalemia. Thus, we have no concerns about our ability to access and recruit the required number of participants for this study. The estimate demographic breakdown of patients at the renal clinic are 95% male with 40% white, 25% black, 20% Hispanic, 10% Asian, and 5% other racial/ethnic background. The planned enrollment is outlined in Table 1.

Table 1. Planned enrollment report

Racial Categories	Ethnic Categories				Total
	Not Hispanic or Latino		Hispanic or Latino		
	Female	Male	Female	Male	
American Indian/ Alaskan Native	0	0	0	0	0
Asian	0	1	0	0	1
Native Hawaiian or Other Pacific Islander	0	0	0	0	0
Black or African American	0	2	0	1	3
White	1	3	0	1	5

More than 1 race	0	1	0	0	1
Total	1	7	0	2	10

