8) Study endpoints

Among 10 stages 3-4 CKD patients with persistent, mild hyperkalemia, we will evaluate, in a quasi-experimental, controlled feeding study, the efficacy of patiomer for maintaining normal serum potassium concentrations when following a plant-rich diet that includes high-potassium fruits and vegetables, as well as the effects of this diet on health outcomes. The participants will be transitioned gradually to a plant-rich diet, as outlined further below.

The interventions will be evaluated primarily in terms of serum potassium concentrations, but health outcomes will also be assessed, including blood pressure, gastrointestinal symptoms, and fasting concentrations of phosphorus, calcium, magnesium, albumin, glucose, insulin, cholesterol, LDL-cholesterol, HDL-cholesterol, triglycerides, urea nitrogen, bicarbonate and C-reactive protein. For all parameters, baseline values will be compared to values at the end of each diet phase (weeks 2 and 4).

9) **Procedures involved**

a. Design.

We will conduct an unblinded, quasi-experimental, controlled feeding study, which will be coordinated through the New York University – Health and Hospitals Corporation Clinical and Translational Science Institute (CTSI). Throughout the study, participants will be prescribed patiromer by the study nephrologist ([name]), which will be administered through the CTSI pharmacy. After a 1-week stabilization period, in which participants are prescribed Patiromer while following their usual diets, the feeding component of the study will occur in two phases. During the first phase (week 2), participants will be transitioned to a plant-rich renal diet, which contains moderate protein (10-15% of kcal), restricts dairy products (≤ 1 serving/day), and eliminates high-potassium fruits and vegetables. During the second phase (weeks 3 and 4), the diet will be altered to provide at-least half of fruits and vegetables from high-potassium sources. To reduce participant burden, meals will be delivered to participants by Portable Chef (New York, NY) three times per week.

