A descriptive analysis of all data collected will be performed using appropriate graphical and numerical exploratory data techniques. The information obtained from this preliminary investigation of the data will be used to: (1) assess data quality and completeness, (2) describe univariate distributions at baseline and follow up, and (3) create summary statistical data for outcome variables at each time point, including the proportion of participants with hyperkalemia. We will identify features of the data that may necessitate special analytic methods (e.g., excess zeros, missing data, departures from distributional assumptions, outliers).

For analytic analyses, we will examine: (1) changes in outcome variables (blood pressure, gastrointestinal symptoms, and fasting concentrations of potassium, phosphorus, calcium, magnesium, albumin, glucose, insulin, cholesterol, LDL-cholesterol, HDL-cholesterol, triglycerides, urea nitrogen, bicarbonate and C-reactive protein), and covariates (weight, medications, dose of Patiromer) between baseline and the end of each diet phase, and (2) relationships between the changes in outcome variables and covariates. Changes in study outcomes will be graphically depicted using means \pm SD or median (IQR) as measures of central tendency and variance. Changes in study outcomes will be analyzed using repeated-measures analysis of variance with post-hoc Tukey HSD test. Because of the small sample size, covariates will be reported instead of being included in a multivariable model. Depending on the types of covariate and outcome of interest, subgroup analyses may be performed with these participants removed from the dataset. For example, if a participant's dose of phosphorus binder medications changed during the study, the analysis of phosphorus concentrations would be conducted with/without this participant. Given the short duration of this study (4 weeks) in relation to typical monitoring of patients with stage 3B-4 CKD, we expect that that few, if any, subgroup analyses will be required.

12) Provisions to Monitor the Data to Ensure the Safety of Subjects

Protection against Risk.

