Prior to the intervention, participants will receive education on the signs and symptoms of hyperkalemia; muscle weakness, abnormally slow or rapid heart rate, and heart palpitations (from Patient education: Hyperkalemia (the basics); UpToDate.com)⁶. Participants will be directed to monitor themselves for these conditions, and to go to the emergency room if they start experiencing them, making sure to notify the emergency department staff about their participation in the study. Standard treatment for acute episodes of hyperkalemia includes intravenous infusions of calcium gluconate and glucose/insulin, often followed by polystyrene sulfonate or emergent dialysis to remove excess potassium. The emergent treatment of adverse events will be at the discretion of the attending physician. In the event of any admission to the emergency room (even if determined to be unrelated to hyperkalemia), participants will be asked to alert the study PIs as soon as possible.

The intervention contains several features to lower the risk of hyperkalemia. For one, the research diets will be prepared for participants to provide control over the dietary potassium exposure. We will use the feeding study approach that gradually increases dietary potassium in a step-wise manner in order to prevent large shifts in dietary potassium intake. During phase I, participants will be stabilized on a plant-rich diet that restricts dairy products and excludes fruits and vegetables that are high in potassium. This closely approximates the current dietary recommendations for CKD patients with hyperkalemia, but does include plant-based foods from the Protein Foods Group (legumes, nuts, seeds), which are high in potassium (>200 mg/serving). However, compared to the typical Western diet, plant-rich diets are more alkaline, and are higher in fiber, factors that are thought to help control serum potassium concentrations⁴. After a week of consuming this diet, high-potassium fruits and vegetables will be introduced, and make up half of the fruit and vegetable servings. We will closely monitor participants’ adherence to the research diets through daily food records to ascertain their adherence with the study diets – participants that are determined to be non-adherent with the research diets at the end of phase I (defined in section 14) will be withdrawn from the study.

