Another intervention feature to lower the risk of hyperkalemia is the close monitoring of participants’ serum potassium concentrations to adjust the dose of patiomer (10.a.i. Table 2). We will measure serum potassium concentrations as per current patiomer recommendations (weekly), and samples will be processed through the Tisch Laboratory, and the results sent to the CTSI Pharmacy for review. If values are abnormally high or rapidly increasing towards hyperkalemia (10.a.i. Table 2), the study nephrologist ([name]) will be immediately contacted. Because hemolysis can cause artificially elevated serum potassium values, participants with abnormally high or rapidly increasing concentrations of serum potassium will have another blood test to confirm their serum potassium concentrations.

In addition to risks associated with hyperkalemia, there are potential risks related with patiromer use. In a sample of 734 patients treated with patiromer, the most common AEs were constipation (7.2%), hypomagnesemia (5.3%), diarrhea (4.8%), nausea (4.8%), abdominal discomfort (2.0%) and flatulence (2.0%). It is likely that the most common of these AEs (constipation, hypomagnesemia, diarrhea) would be attenuated by a plant-rich diet, which contains higher amounts of fiber and magnesium compared to the typical Western diet. The less common adverse events (abdominal discomfort, flatulence) may be exacerbated by the higher intakes of dietary fiber. These potential AEs will be assessed at the end of each week through the gastrointestinal symptoms questionnaire, and blood testing at the end of phase I and II (for hypomagnesemia). Patiromer also has the potential to bind to other medication, reducing their absorption. This will be mitigated by directing patients to take patiromer once daily, and at least 3 hours away from other medications.

It is unlikely that women and men with stages 3-4 CKD will become pregnant or impregnate someone. Additionally, we will exclude anyone who is planning on becoming pregnant from the study. As part of our Clinical Trial Agreement with Relypsa, Inc., we will report any pregnancies (whether female or male impregnating a female) to Relypsa, Inc. In addition, because the patiromer and the research diets are untested in pregnant women, we will withdraw women who become pregnant during the study period.

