Lastly, participants in the study are at risk of breaches of confidentiality. A variety of measures will be used to prevent breaches of confidentiality. First, all study staff will be trained in the NYULMC Practice Fundamentals, which include training in issues of confidentiality. Additionally, all study staff will be required to sign a confidentiality agreement. Although study staff may have access to sensitive information about the participant as recorded in their medical record, only that information pertinent to the study outcomes will be abstracted from the medical record. Data will be maintained as described above (see section 12). We will take steps to avoid participants' perceptions of coercion in the recruitment process.

13) Withdrawal of subjects

As mentioned previously, participants may be withdrawn from the study without their consent in the event that they become pregnant, or they are non-adherent with the research diets. Non-adherence to the research diets will be defined as consumption of >25% of energy from non-research diet foods, which will be assessed at the end of phase I of the study. In the event that involuntary withdrawal is required, participants will be referred back to their treating physician of record for evaluation and management. Data collection will cease at the time of withdrawal.

14) Risks to subjects

Most of the risks associated with this study are outlined in section 13 along with corresponding measures to protect against these risks (include hyperkalemia, patiromer side effects and interactions with medications, and breach of confidentiality). Blood tests will be drawn for this study, which are sometimes accompanied by bruising, bleeding, and minor tenderness at the puncture site. Participants will be made aware of all of these risks prior to enrolling in this study.

15) Potential Benefits of the Proposed Research to the Subjects and Others

Participants may experience some temporary improvement in cardiometabolic risk factors and serum potassium concentrations related to intervention; however, this is not guaranteed. Moreover, any temporary improvements in these conditions are unlikely to have any lasting benefits to participants.

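### Repeated-measures ANOVA would by default drop participants withdrawn for non-adherence from the baseline-to-week-2 comparison, although their week 2 values are due to be collected

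*Combined protocol and SAP*

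**What the plan says.** **Withdrawal.** Section 12 (Protection against Risk) states that "participants that are determined to be non-adherent with the research diets at the end of phase I" will leave the study. Section 13 gives the criterion: "Non-adherence to the research diets will be defined as consumption of >25% of energy from non-research diet foods". It adds: "Data collection will cease at the time of withdrawal". Section 12 words removal as certain, whereas section 13 words it as possible.

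**Schedule.** Section 8 and Table 4 place the ends of the two diet phases at weeks 2 and 4. The opening of section 9.b gives weeks 1 and 3, but the detailed items below it and Table 4 use 2 and 4, as I do here. By week 2, a participant is due to have given a reference value (screening for potassium, baseline for the rest) and a week 2 value. Potassium and the gastrointestinal questionnaire are also due at week 1.

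**Analysis.** Section 11 states: "Changes in study outcomes will be analyzed using repeated-measures analysis of variance with post-hoc Tukey HSD test". It defines no analysis set and no method for missing values. It does plan descriptive summaries of everything collected, at each time point, and lists missing data among the features that may call for special methods.

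**Size.** Section 5 states: "We will recruit a total of 10 individuals to the study". No power, SD, significance level or expected dropout is given.

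**The concern.** The withdrawal rule creates a predictable pattern: reference and week 2 values present, week 4 absent. Classical repeated-measures ANOVA needs every participant at every time point. Someone withdrawn after week 2 therefore disappears from the whole model, including a week 2 contrast to which they could have contributed fully.

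Two things are at stake. One is precision, because each withdrawal is a tenth of the sample. The other is possible selection: the week 2 test would describe only those who reached week 4. If the reasons for eating other food are related to potassium, symptoms or another outcome, the week 2 mean among completers differs from the mean among all who were measured.

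**Working it through.** There is no power or precision figure in the plan to reproduce. Table 1 does sum to 10 by racial category (1 + 3 + 5 + 1) and by column (1 + 7 + 0 + 2). The number withdrawn, k, is not given, so I assume a range of 0 to 3.

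**1. Does the method drop these participants?** A test data set of 10 people and three time points, with the third value missing for 2, was given to a standard repeated-measures ANOVA routine (AnovaRM in statsmodels). It refused the data as unbalanced. In practice the analyst would have to remove the incomplete participants or change method.

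**2. What is lost?** With n = 10 − k complete cases and three time points:
- error df = (n − 1) × (3 − 1)
- collected laboratory or blood pressure values left unused (baseline and week 2) = 2k
- 95% half-width for a mean change, in SDs of that change = t(0.975, n − 1)/√n. This is a simple one-sample yardstick, not the ANOVA's pooled-error interval.

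| k | n | error df | unused values per outcome | half-width (SD) |
|---|---|---|---|---|
| 0 | 10 | 18 | 0 | 2.262/√10 = 0.715 |
| 1 | 9 | 16 | 2 | 2.306/√9 = 0.769 |
| 2 | 8 | 14 | 4 | 2.365/√8 = 0.836 |
| 3 | 7 | 12 | 6 | 2.447/√7 = 0.925 |

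For k = 2 the interval is 0.836/0.715 = 1.17 times as wide. For the gastrointestinal questionnaire, up to 3k collected values (baseline, weeks 1 and 2) go unused.

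**3. How large could the bias be?** Let D be the mean week 2 change in those withdrawn minus that in those retained. The mean over all 10 equals the retained mean plus (k/10) × D, so the complete-case result is too low by (k/10) × D. With k = 2:
- D = 0.5 SD: too low by 0.10 SD
- D = 1 SD: too low by 0.20 SD
- D = 0: no bias
- D = −0.5 SD: too high by 0.10 SD

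**4. Simulation.** A true change of 0.5, between-person SD 1 and within-person SD 0.7 were assumed, with 400 runs per setting.

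| Withdrawal in relation to week 2 symptoms | mean number withdrawn | week 2 change, complete cases |
|---|---|---|
| unrelated | 1.7 | 0.49 |
| moderately related | 2.2 | 0.40 |
| strongly related | 3.0 | 0.33 |
| inversely related | 2.2 | 0.57 |

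Using all collected week 2 values gave 0.48 to 0.50 in every setting. At week 4, complete cases gave 0.49 to 0.52 and a random-intercept mixed model 0.49 to 0.51. The two hardly differ there, but the simulation includes no personal intolerance that persists to week 4.

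**The case against.** **The plan never says these data are discarded.** This is correct. The loss is a default of the method, not a stated rule, and the descriptive summaries would still show everyone measured. But the tests remain complete-case unless something else is specified. A special method chosen after the data are seen is a weak substitute when the protocol itself creates the missing values.

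**An effect in adherent participants is a legitimate target.** Section 15 puts safety and internal validity ahead of generalizability, and for a proof-of-concept feeding study that is defensible. It does not rescue the default, however. Complete-case analysis selects on having a week 4 value, whatever the reason for lacking one, and section 11 does not state an adherent-only target.

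**Few may be withdrawn.** Section 4 excludes people unable or unwilling to follow the diets, section 29 has candidates review the menus, and section 9.a.ii permits substitutions. The number could be zero, and then nothing is lost.

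**The direction of any symptom bias is not known.** Section 12 does say: "The less common adverse events (abdominal discomfort, flatulence) may be exacerbated by the higher intakes of dietary fiber". The sentence before it expects constipation and diarrhea to be attenuated, and both are covered by the questionnaire. Those who eat less of the study diet may also have fewer diet-related symptoms. This objection stands in full.

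**Safety reporting is separate.** Adverse events are reported whatever the ANOVA includes. This also stands, but it does not repair the outcome analysis.

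**The order of events at week 2 is not stated.** Adherence is judged at the end of phase I, and the documents do not say whether the week 2 tests come first. The point assumes that the scheduled visit is completed.

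**Conclusion.** The point holds as a weakness in the choice of analysis. The stated method would by default leave collected reference and week 2 values out of the week 2 test, and a better method is readily available. The loss of precision is definite if anyone is withdrawn: with 2 of 10, the half-width goes from about 0.72 to 0.84 SD. Bias at week 2 is possible but conditional. It needs at least one withdrawal and a relation between withdrawal and the outcome, and its sign could go either way. The gain from the change lies mainly at week 2.

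A reader might infer more than the documents support:
- *That gastrointestinal symptoms are understated, or that results cover only those who tolerated the diet.* Non-adherence is defined by share of energy, not tolerance, and no passage links symptoms to eating other food.
- *That a success rate would be inflated by a smaller denominator, for example 8 of 8 instead of 8 of 10.* Successful transition is not a planned endpoint. Section 8 compares outcome values, and section 11 adds only a descriptive proportion with hyperkalemia.
- *That removal is discretionary and decided with outcomes in view.* Section 13 refers back to earlier text and sets a numeric threshold, so the looser verb is more likely a wording mismatch. It should still be reconciled.

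**What to change.** The withdrawal of participants from the diet need not change for this purpose. The changes are to the text:

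1. In section 11, replace repeated-measures ANOVA with a likelihood-based mixed model for repeated measures, using every collected visit and a small-sample degrees-of-freedom correction such as Kenward-Roger. Name the covariance structure and a simpler fallback. An unstructured matrix for three visits has 3 × 4/2 = 6 parameters, which is a lot for 10 people.
2. State that the baseline-to-week-2 comparison (screening to week 2 for potassium) includes everyone with a week 2 value, whatever their adherence.
3. Report the number of withdrawals and the reasons beside the proportion with hyperkalemia at each time point.
4. Describe week 4 results as applying to participants who continued on the diet.
5. Reconcile sections 12 and 13 on whether non-adherent participants will or may be withdrawn.

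No extra visits, samples or participants are needed. The cost is slightly more analysis work and reliance on a missing-at-random assumption for week 4. The data cannot test that assumption, since nothing is collected after withdrawal.
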